1. ABSTRACT

Smoking is the leading preventable cause of death in New York City (NYC), and people with low income, including many immigrant populations, living in NYC are more likely to suffer from smoking-related mortality. However, there have been limited efforts to develop tobacco use programs specifically for low-income or immigrant populations. Prior research has found that low-income smokers face unique barriers to cessation, including financial distress, negative outcome expectancies, depressed mood, an externalized locus of control, and an increased focus on immediate needs at the expense of delayed goals. Financial counseling is effective at improving financial knowledge and outcomes, and offers the opportunity to reinforce the financial rewards of quitting while simultaneously improving the financial circumstances and associated barriers to abstinence in low-income smokers. We propose a pilot project that will evaluate an innovative program that integrates financial counseling with smoking cessation counseling for low-income and immigrant smokers at Bellevue Hospital Center and Lutheran Medical Center. The project will achieve the following specific aims: (1) Estimate the acceptability of the integrated program and its effect on participants' financial stress, mental wellness, quit attempts, and abstinence from cigarettes; (2) Estimate the per-patient cost of the integrated program; and (3) Identify barriers and facilitators toward wide-scale implementation of the program model. To accomplish these aims, we will conduct a two-arm randomized, wait-list control study. We will recruit 600 smokers to complete a 9-week intervention that integrates financial management and smoking cessation counseling. Participants will be randomized (300 per arm) to receive the intervention immediately after enrolling (Intervention Arm) or 6 months later (Waitlist Control Arm). Both arms will receive nicotine replacement therapy (NRT) for four weeks during their time in counseling. We will survey patients at baseline, 6 and 12 months to assess outcomes and their satisfaction with treatment. Additionally, we will recruit and interview hospital staff (N=5 per site, 10 total) to assess their perceptions regarding barriers and facilitators toward downstream implementation of the intervention.

2. PURPOSE OF THE STUDY AND BACKGROUND

2.1 Background

Smoking is the leading preventable cause of death in New York City (NYC), and people with low-income, including many immigrant populations, living in NYC are more likely to suffer from smoking-related mortality. Further, immigrants in NYC – particularly those of Chinese, Dominican, Mexican, and Puerto Rican descent – often live in poverty, placing them at distinctly high risk for smoking, morbidity, and mortality. Indeed, previous research has found that rates of smoking among low-income households are three times higher than those among high-income households, and this income disparity in tobacco use has persisted over time. However, despite the chronic income disparity in tobacco use and high rates of smoking among immigrant populations, there have been limited efforts to develop tobacco use programs specifically for low-income or immigrant populations.

Prior research has found that low-income smokers face unique barriers to cessation, including financial distress, negative outcome expectancies, depressed mood, an externalized locus of control, and an increased focus on immediate needs at the expense of delayed goals. Of particular concern is that tobacco use can exacerbate financial strain by limiting funds to pay for other goods and services. In New York, smoking households spend approximately \$1,100 year on tobacco – money that could otherwise be spent on household essentials such as food, clothing, and health care. Previous research has found that smoking households are more likely to experience food and housing insecurity and spend a larger proportion of their budget on tobacco than on health care. In NYC in particular, smokers living in the lowest income level can spend almost 30% of their budget on cigarettes. Our prior work has found that tobacco cessation is associated with reduced spending on alcohol and entertainment, and with increases in household savings. Thus, tobacco cessation can improve both the health and the financial well-being of low-income smokers.

Evidence supports the effectiveness of financial incentives to increase abstinence rates in low-income populations by providing reinforcement for quitting. However, providing cash payments for quitting may not produce sustained behavior change and raises ethical concerns over the exploitation of low-income populations' economic vulnerability without providing assistance with their underlying financial conditions. In contrast, financial counseling is effective at improving financial knowledge and outcomes, and offers the opportunity to reinforce the financial rewards of quitting while simultaneously improving the financial circumstances and associated barriers to abstinence in low-income smokers. Money management counseling has been shown to improve health and economic outcomes in patients using cocaine and/or alcohol. We aim to adapt this model by integrating money management counseling with smoking cessation counseling.

2.2 Aims

1. Estimate the acceptability of the integrated program and its effect on participants' disposable income, savings, financial stress, mental wellness, and abstinence from cigarettes.
2. Estimate the per-patient cost of the integrated program.
3. Identify barriers and facilitators toward wide-scale implementation of the program model.

2.3 Study Design

We will conduct a two-arm randomized, wait-list control study. We will recruit 610 participants total: 600 patient participants and 10 staff participants. We will recruit 600 smokers to complete a 9-week intervention that integrates financial management and smoking cessation counseling. Participants will be randomized (300 per arm, stratified by site) to receive the intervention immediately after enrolling (Intervention Arm) or 6 months later (Waitlist Control Arm). Both arms will receive nicotine replacement therapy (NRT) for four weeks as part of their time in integrative counseling. We will survey participants at baseline, 6 months and 12 months to assess outcomes and their satisfaction with treatment. The first 150 enrollees will complete an additional 2 month follow up survey. Additionally, we will recruit and interview hospital staff (N=5 per site, 10 total) to assess their perceptions regarding barriers and facilitators toward downstream implementation of the intervention.

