2.4 Sites

The study will be conducted at two sites:

2.4.1 *Bellevue Hospital Center* is the largest public hospital system in the United States and is one of the New York City Health and Hospitals Corporation's member institutions. It is also the nation's oldest public hospital, established in 1736 as a 6-bed infirmary. The Adult Primary Care Center at Bellevue Hospital will serve as the site for recruitment from Bellevue. The Center provides over 60,000 continuity visits per year to approximately 28,000 active patients with a variety of chronic conditions.

2.4.2 *Lutheran Medical Center*, Lutheran, which merged with NYULMC January 1, 2016, is the largest Federally-Qualified Health Center in NY State and 2nd largest in the US. Its 109 physicians, 43 NPs and PAs, 19 care managers and 4 community health workers care for >100,000 patients at 65 practice sites. As a level 3 patient-centered medical home, the Lutheran network offers a full range of health and dental care, including adult and family medicine, behavioral health, chronic disease management, comprehensive HIV/AIDS services, pediatrics and specialty services.

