3.5 Eligibility Criteria

3.5.1 Patient participants:

- 1) age ≥ 18 years
- 2) Has smoked a cigarette in the past 30 days, even a puff
- 3) Interested in receiving smoking and financial counseling
- 4) Self-reported income below 200% of the current federal poverty level for a given household composition
- 5) New York City resident
- 6) English or Spanish language
- 7) Able to provide informed consent, and
- 8) Does not have a representative who manages his/her funds (to ensure the participant has the ability to manage household money). We will exclude participants who report being pregnant or breastfeeding (unable to receive NRT).

3.5.2 Hospital staff participants:

- 1) Must be current medical or non-medical provider or administrator at Bellevue Hospital or NYU Lutheran Medical Center

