Third, at the Bellevue site, we will receive referrals from the hospital's regular smoking cessation program. The smoking cessation program will let patients know about the study and give them the study flyer (Appendix A). The program will ask if they are interested in being referred to our study to learn more about the study. For patients who give permission to be referred, the Bellevue smoking cessation program will send our study team an NYUMC encrypted email with the name and preferred contact information. To all referred patients, a study RA will send a letter (Appendix B) and the recruitment flyer (Appendix A). Two weeks after mailing the materials, an RA will call the patients to discuss the study, screen interested patients for eligibility, and schedule eligible participants for an appointment to complete an IRB-approved informed consent process. All identifiable screener data for patients who are deemed ineligible or who do not wish to participate in the study will be destroyed. We will only keep itemized screener data to report to the funding agency, though no PHI will be saved and we will only label participants with a pre-screening number.

Fourth, we will work with medical center IT to set up a consult in EPIC that allows physicians to refer Lutheran patients to the program. Providers will be given an overview of the study and eligibility criteria prior to implementing the EPIC consult, so that they may filter some of the referrals received. If a patient is deemed eligible for referral, physicians will inform their patients that someone from the study team will contact them within the next two weeks to screen for study eligibility. Providers will also have copies of our study flyer (Appendix A) to hand out to patients who are interested, so the patient may also reach out directly to the research coordinator as directed by the flyer. Each day, a study team member will check EPIC for a list of patients referred by their providers. An RA will contact the patients to screen for eligibility. Those who are eligible will be scheduled for a consent appointment. Patients who are ineligible to participate in the study will be referred to the NY State Quitline. All identifiable screener data for patients who are deemed ineligible or who do not wish to participate in the study will be destroyed. We will only keep itemized screener data to report to the funding agency, though no

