4.5 Patient Participant Randomization

At the conclusion of the baseline survey, the RA will open a study database on a computer that he/she will have at the time of informed consent and enter a randomly assigned study ID number. The database will then use a random-number generator (developed under the supervision of the statistician) to assign the patient participant to one of the study arms. The database will store the randomization results and display the results on the screen for the RA, who will inform the participant of his/her group assignment, discuss the details of the assigned intervention, and schedule the patient participant for his/her intervention's first session and follow-up assessments.

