5.1 Data Analysis

To evaluate the acceptability and feasibility of the integrated intervention, we will calculate the number of counseling sessions completed and satisfaction with treatment, which we will summarize descriptively using count and frequency statistics. We will calculate additional measures of study feasibility and acceptability, including the eligibility rate among people screened, enrollment rate among those eligible, reasons for ineligibility or refusal, and the proportion of participants who would recommend the intervention to other smokers. To estimate the effect of the integrated intervention on outcomes we will use generalized estimating equations (GEE) to model the main effects of time (baseline to 6 and 12 months)

and treatment group, and the interaction of time and treatment, on each outcome. GEE will allow us to determine whether intervention effects are present and whether they change over time.

We will also calculate and sum all time and costs of administering the interventions. Each intervention staff member will record their activity in a web-based intervention tracking system (using REDCap). Staff prospectively input detailed information for a 1-week sample of their activities and associated time required on a monthly basis. Those recording their time and activities have flexibility to add or tailor their entry form to match their exact activities. We will assign a dollar value for each unit of staff time based on the wage and fringe rate of those who perform the activity using regional labor rates from the US Bureau of Labor Statistics. We will also keep track of medications ordered and used by participants, which we will assign a dollar value to using Red Book, a wholesale pharmaceutical pricing index. Once all costs are compiled and summed, they will be adjusted to constant dollars using the medical care component of the Consumer Price Index.

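### Randomisation is stratified by site but the GEE in 5.1 has no site term, so standard errors for follow-up arm contrasts can be slightly too wide (minor)

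*Combined protocol and SAP*

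**What the plan says.** Section 2.4 of the combined protocol and SAP states: "The study will be conducted at two sites". Section 2.3 makes site the stratification factor: "Participants will be randomized (300 per arm, stratified by site) to receive the intervention immediately after enrolling".

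Section 4.5 describes the mechanics: "The database will then use a random-number generator (developed under the supervision of the statistician) to assign the patient participant". It mentions neither strata nor blocks, so it does not say how site enters the allocation.

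The only model for effects on outcomes is in 5.1: "generalized estimating equations (GEE) to model the main effects of time (baseline to 6 and 12 months", continuing "and treatment group, and the interaction of time and treatment, on each outcome". The model names neither site nor any other covariate, and no other section adds site to the analysis. Section 5.1 also gives no effect measure, link function or definition of abstinence.

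Section 3.5 requires of every patient: "Has smoked a cigarette in the past 30 days, even a puff".

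**The concern.** Stratifying by site removes chance imbalance between sites from the comparison of arms. An analysis without site does not use that gain, because the spread between sites stays in the residual variance. The reported standard error then describes a noisier design than the one that was run, and the test is slightly conservative.

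Three conditions are needed.

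- **(a) Site predicts the outcome.** The documents do not show this. It is plausible, since some recruitment differs by site. In 4.2, one route reads "Third, at the Bellevue site, we will receive referrals from the" hospital's own cessation program, and another is to "set up a consult in EPIC that allows physicians to refer Lutheran patients to the program". The MyChart messages go only to Brooklyn patients. Flyers, record searches, waiting-room approaches and all eligibility criteria are common to both sites.
- **(b) The arms are balanced within site.** Section 2.3 implies this; 4.5 does not confirm it.
- **(c) The contrast is a follow-up level, or the site difference changes over time.** If abstinence is defined over 30 days, (c) follows from (a). The eligibility rule makes baseline abstinence zero at both sites, so any site difference must arise after baseline.

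Aim 1 is to estimate effects, so the width of the intervals is part of the result.

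**Working it through.** **Inputs.** From the documents: 600 patients, 300 per arm, two sites (2.3, 2.4). The arithmetic agrees: 300 + 300 = 600. The plan states no power, standard error, outcome rate, SD or alpha, so there is no planned precision figure to reproduce. Everything below on site effects is assumed: rates and SD differences as shown, complete data, no treatment effect, nominal two-sided 5% tests and, unless stated, 300 patients per site.

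**1. Abstinence at a follow-up, arms balanced within site.** Let p1 and p2 be the site rates and p their mean.

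- Unadjusted variance of the risk difference: 2·p(1−p)/300.
- Site-stratified variance: 2·[½p1(1−p1) + ½p2(1−p2)]/300.
- 8% v 12%: SE ratio √(0.0900/0.0896) = 1.002.
- 5% v 15%: √(0.0900/0.0875) = 1.014. SE 2.45 v 2.42 points; 95% half-width 4.80 v 4.73.
- 5% v 25%: √(0.1275/0.1175) = 1.042. SE 2.92 v 2.80 points; half-width 5.71 v 5.49.
- With sites of 200 and 400, either way round, the excess is 0.2%, 1.1–1.5% and 3.1–4.6%.

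Simulation compares the mean reported unadjusted SE with the actual SD of the estimate.

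- 8% v 12%: ratio 0.997 to 0.999 in runs of 200,000 to 1,000,000 trials, type I error 5.0–5.1%. There is no excess. The usual unpooled SE is itself low by about 1/(2·300) = 0.17%, which uses up the 0.2% from the formula.
- 5% v 15%: ratio 1.012, type I error 4.8%.
- 5% v 25%: ratio 1.038 to 1.040, type I error 4.1–4.2%.

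**2. Continuous outcome at a follow-up, balanced within site.** For a site difference of d SD, the SE ratio is √(1 + d²/4).

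- d = 0.2: √1.01 = 1.005, true type I error 4.9%.
- d = 0.5: √1.0625 = 1.031, 4.3%.
- d = 0.8: √1.16 = 1.077, 3.5%.

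A GEE simulation (d = 0.5, within-person correlation 0.5, 4,000 runs) gave mean SEs of 0.0840 without site and 0.0815 with site. The ratio, 0.0840/0.0815 = 1.031, agrees.

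**3. Continuous time-by-treatment contrast, balanced within site.** Here d is the change in the site difference and ρ the within-person correlation. The SE ratio is √(1 + (d²/4)/(2(1−ρ))).

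- d = 0 (constant site difference): 1.000.
- d = 0.2: 1.004, 1.005 and 1.008 for ρ = 0.3, 0.5 and 0.7.
- d = 0.6: 1.032, 1.044 and 1.072.

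A site main effect alone does not correct this contrast. With an assumed 0.5 SD change by 6 months, the interaction SE was 0.0840 with or without it, against an actual SD of 0.0814. Site-by-time is needed.

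**4. Simple allocation, not balanced within site.** The unadjusted SE is about right: within 0.4% of the actual SD in all three abstinence cases, with type I error 5.0–5.1%. Adjustment lowers the actual SD from 2.448 to 2.445, from 2.452 to 2.421 and from 2.922 to 2.804 points.

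**5. Can the adjusted abstinence model be fitted?** On a 30-day definition baseline abstinence is zero in every arm and site, so the baseline log-odds have no finite estimate. In a test fit, a logit GEE including baseline gave standard errors in the thousands even without site, and undefined ones with site and site-by-time. The same model on the 6- and 12-month data fitted normally.

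**The case against.** The strongest reply is that little is at stake. The documents establish neither (a) nor (b), and if the generator allocates without regard to site, the unadjusted SE is not too wide at all. That stands, and it is why the point is minor.

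A second reply is that 5.1 relies on the time-by-treatment interaction, from which a constant site difference cancels. This stands for continuous outcomes with complete data. It does not cover abstinence on a 30-day definition, or a site difference that changes over time.

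A third is that putting site and site-by-time into every outcome model as 5.1 lays it out would fail for abstinence. This also stands, as step 5 shows, and it limits the fix.

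A fourth is that site may not be obvious for everyone: 3.5 does not require being a patient at either hospital, and newspaper, Facebook and word-of-mouth recruitment are open. No section says how such people are assigned to a site. Stratified allocation does, however, require a site to be recorded before assignment.

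Two stronger readings are tempting. A reader might infer that leaving out site biases the treatment effect or makes the tests invalid. It does neither: randomisation protects the estimate, and any error in the SE of practical size is on the conservative side. A reader might also infer from 4.5 that allocation is not really stratified. Section 4.5 is silent on strata; it does not describe simple allocation, and silence does not contradict 2.3.

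**Conclusion.** The mismatch is real and minor. Site is a design factor in 2.3 and is absent from the only outcome model in 5.1. If site predicts the outcome and the arms are balanced within site, reported standard errors for follow-up arm contrasts can be too wide by roughly 0 to 1.5% for modest assumed site differences and 3% to 8% for large ones. The same ranges cover the continuous time-by-treatment contrast when the site difference changes over time. Without balance within site there is no material excess, and adjustment only gains a little precision. These sizes rest on assumed site effects, since the documents report none. Adjustment is worth adopting because it is nearly free and because naming it in advance keeps it from being chosen after the results are seen.

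**What to change.** In 5.1:

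- **Continuous outcomes:** add site and site-by-time as covariates in the GEE.
- **Abstinence:** fit the site-adjusted model to the 6- and 12-month data only, or use another specification that can be estimated. If a logit link is used, adding site turns the odds ratio into a site-conditional one. A site-standardised risk difference at each follow-up is one way to keep a marginal comparison of arms.
- **Definition of site:** use the site recorded for stratification at randomisation.

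One sentence in 4.5 saying how site enters the allocation would settle condition (b) and match 2.3.

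The cost is up to three extra parameters (site, site-by-6-months, site-by-12-months) with 600 participants, a standardisation step if that option is taken, and no new data.

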2.4 Sites

The study will be conducted at two sites:

2.4.1 *Bellevue Hospital Center* is the largest public hospital system in the United States and is one of the New York City Health and Hospitals Corporation's member institutions. It is also the nation's oldest public hospital, established in 1736 as a 6-bed infirmary. The Adult Primary Care Center at Bellevue Hospital will serve as the site for recruitment from Bellevue. The Center provides over 60,000 continuity visits per year to approximately 28,000 active patients with a variety of chronic conditions.

2.4.2 *Lutheran Medical Center*, Lutheran, which merged with NYULMC January 1, 2016, is the largest Federally-Qualified Health Center in NY State and 2nd largest in the US. Its 109 physicians, 43 NPs and PAs, 19 care managers and 4 community health workers care for >100,000 patients at 65 practice sites. As a level 3 patient-centered medical home, the Lutheran network offers a full range of health and dental care, including adult and family medicine, behavioral health, chronic disease management, comprehensive HIV/AIDS services, pediatrics and specialty services.

3. CHARACTERISTICS OF THE RESEARCH POPULATION

There are two groups of participants in the study: Patient participants and hospital staff participants.

